A Randomized Controlled Trial With Retention Testing to Determine the Most Effective Intervention for
Hemorrhage Control Readiness for Laypersons: The PATTs Trial

January 29, 2018

Study Protocol and Statistical Analysis

a. Study design:

- a. Prospective, randomized, multi-arm, open-label trial with follow-up retention testing

b. Location:

- a. Gillette Stadium, Foxborough, Massachusetts, USA.

c. Consent:

- a. Participation in the study was voluntary and oral consent was obtained from all subjects. A fact sheet was provided to all participants.

d. Inclusion/Exclusion criteria:

- a. Adult (18 years and above) volunteers with no prior hemorrhage control training or experience were included in the trial.
- b. Anyone with previous formal hemorrhage control or tourniquet training was excluded from the trial analysis.

e. Randomization:

1. Eligible study subjects were randomized into the following arms using block randomization such that for every four participants, one was randomized to each of the four arms:

- i. **Control arm:** Study subjects in this arm of trial received no intervention (no training or access to point-of-care prompts) to assess baseline competence in hemorrhage control.
- ii. **Experimental arm 1:** Study subjects in this arm were given the American College of Surgeons Bleeding Control Basic (B-Con) in-person training course by qualified instructors. This curriculum was developed by a collaboration between American College of Surgeons and the Hartford Consensus.⁹ The session included a multimedia presentation in a class format that included some background information about extremity hemorrhage and potential benefits of immediate first-response and hemorrhage control, steps to take in a mass casualty scenario and instructional videos on hemorrhage control modalities and their appropriate use. This was followed by hands on training in hemorrhage control, with 1:4, instructor to trainee ratio.

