- iii. **Experimental arm 2:** Study subjects in this arm received a commercially available audio bleeding control kit. The kit included diagram and visual aids to identify the correct severity of injury and determine the appropriate method of bleeding control. The kit also had buttons on it to play stepwise audio instructions on application of compression dressing, hemostatic packing and tourniquet application in two languages (English and Spanish). The audio kits were bought at market price and the name of the manufacturer was not mentioned in the manuscript to avoid conflict of interest.
- iv. **Experimental arm 3:** Study participants in this arm of the trial received bleeding control flashcards that contain diagrams and figures to correctly identify the severity of injury and visual instructions on appropriate application of pressure dressing, hemostatic packing and tourniquet.

f. Sample size calculation:

- a. Sample Size calculation was done using Stata v14.1 with 80% power and an alpha level of 0.05. Trial arm paired-comparisons were taken as independent trials and sample size was calculated for each pair. The largest number was taken as the sample size for each arm. The smallest difference in application rate, and the arm used to determine sample size calculation, was between the control and flashcard arm.
 - i. Control group expected application rate 20% based on prior studies
 - ii. Flashcard Proportion expected application rate 44% based on prior studies
- b. Final sample size is 412 with 103 subjects in each arm. This is before exclusion of individuals with prior hemorrhage control training thus, to account for 20% of individuals to report prior training, over 125 individuals will be recruited to each arm.

g. Pre-study questionnaire:

- a. Study subjects were given a pre-trial questionnaire to gather information regarding age, gender, level of education, any prior first-aid training, and if they reported prior first-aid training, whether it included hemorrhage control training. Those individuals who reported prior hemorrhage control training were then asked an open ended question about what that training consisted of. The questionnaire also included questions to determine participants willingness to assist in an emergency and self-reported comfort level in acting as a first-responder in a mass causality scenario. Answers were presented on a Likert-type scale.

h. Post-trial questionnaire:

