1. After testing of the two point of care prompt arms and the control arm, these individuals then underwent the ACS B-Con training from qualified instructors. This training was 45 to 60 minutes long, consisting of an audio-visual presentation with tourniquet application instructions followed by hand-on training under the supervision of an instructor, the same as the B-Con intervention arm.
2. ***Test for retention:***
 - a. 3-9 months after the trial, we planned to test all study subjects with a simulated mass causality scenario for retention of knowledge and skills. This test will be the same as the initial test for competence at tourniquet placement in the trial and the same evaluation form will be used to evaluate the study subjects.

j. Donation of study material:

- a. At the end of the retention study, the bleeding control boxes will be donated to the stadium, to be co-located with AEDs.

1) ***Statistical analysis:***

- a) The primary outcome in our study was the correct application of tourniquets. The main analyses in the randomized study were the pairwise comparisons of the proportion of correct tourniquet application in each of the three intervention arms to the control arm.
- b) In the initial testing phase, the proportion of participants who correctly applied a tourniquet in the three intervention arms were compared to control using three pairwise two-sided Fisher's Exact Test of the three interventions to control in an intent-to-treat analysis (as randomized).
- c) To analyze retention, we performed two pairwise comparisons: 1) all participants tested at retention versus initial control to identify long-term efficacy (correct tourniquet application) compared to no training; 2) participants tested at retention versus initial testing in B-Con randomized arm to identify if there is a significant skill decay 3-9 month after training. Generalized estimating equations z-tests were used in these pairwise tests to account for the repeated measures on participants who were in both the initial and retention phases.
- d) At retention testing, an a priori planned logistic regression analysis was performed to identify any demographic associations with correct tourniquet application between 3 and 9 months after B-Con training. It also assessed for different effects due to the original (randomized) arm in initial testing in case the combination of randomized arm and then

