B-con training had differential effects on correct tourniquet application (although our a priori hypothesis was that there would be no difference). Age was divided into categorical variables creating three groups using previously defined age breaks: young adult [18-35 years old (yo)], middle aged adult (35-55 yo), and older adult (> 55 yo). This model assessed for an association between days since training to retention testing, allowing for a non-linear effect. We assessed for co-linearity, and interactions between variables [age and education, age and sex, age and prior training, sex and education, sex and prior training] and ran diagnostics on the model fit. We used Hosmer and Lemeshow's goodness-of-fit test to evaluate our model.

- e) The Wilcoxon rank sum test was used to compare time to correct tourniquet application across arms (restricted to participants in each arm who correctly applied the tourniquet). Demographic variables for each intervention arm versus control and retention versus control were compared using Wilcoxon rank sum tests for continuous variables and two-sided Fisher Exact tests for categorical variables.
- f) The data on empowerment will be analyzed using descriptive statistics. Likert type data will be analyzed using non-parametric tests (Wilcoxon sign rank, Kruskal-wallis test). Single group repeated measures analysis will be used to analyze the change in empowerment over time. The Likert type data will also further be analyzed by transforming it into dichotomous categorical data with those reporting being very likely or very comfortable being a positive response and anything less than that being recorded as a negative. The various empowerment parameters will be assessed for their relationship with skill efficacy (correct tourniquet application).

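### The retention-versus-control demographic tests assume separate groups although retested control-arm participants are in both, so their p-values are conservative (minor)

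*Combined protocol and SAP*

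**What the plan says.** Statistical analysis item c) sets up two retention contrasts. The first compares "all participants tested at retention versus initial control". For both contrasts it uses generalized estimating equations "to account for the repeated measures on participants who were in both the initial and retention phases".

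The section on the test procedure says that the control arm and the two prompt arms received B-Con training after their first test, and that everyone was to be retested at 3 to 9 months. A control-arm participant who returns therefore counts in the initial control group and again in the retention group.

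Item e) then covers demographics: "Demographic variables for each intervention arm versus control and retention versus control were compared using Wilcoxon rank sum tests for continuous variables". Categorical variables get two-sided Fisher exact tests. Nothing extends the allowance for repeated participants from item c) to these tests.

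**The concern.** The rank sum and Fisher exact tests are built for disjoint groups. Here a control-arm returner contributes the same sex and education, and virtually the same age, to both sides. That shared content makes the two group summaries move together, so their difference varies less than the tests assume. The plan recognises this for the outcome but not for the demographics.

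The retention-versus-control contrast carries the long-term efficacy claim and is not randomized, since it sets whoever came back against the initial control arm. Item e) contains the only demographic comparison planned for that contrast. The regression in item d) models the outcome within the retested group and does not compare it with control. If the p-values run high, the table may look more reassuring than the data warrant.

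**Working it through.** **Inputs from the documents.** Allocation is equal: "for every four participants, one was randomized to each of the four arms". Arm size: "Final sample size is 412 with 103 subjects in each arm". No return rate is given, so *r* is an assumption, taken as equal across arms unless stated.

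**The plan's own figure.** The plan states no figure for the demographic tests. Its sample size does not reproduce: 20% versus 44% at two-sided 0.05 and 80% power needs 59 per arm (67 with continuity correction, 66 by exact Fisher power), and 103 per arm gives about 96% power. This does not matter here, because arm size cancels from the ratio below.

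**Variance with overlap.** Let n be the control arm size. The retention group has 4rn people, of whom rn are control returners. For a difference in means or proportions with common variance, in units of that variance:

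- assumed by an independent-sample test: 1/n + 1/(4rn) = (1/n)(1 + 1/(4r))
- true: the same minus 2·rn/(n·4rn) = (1/n)(0.5 + 1/(4r))
- ratio, true/assumed: (0.5 + 1/(4r)) / (1 + 1/(4r))

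The standard error is overstated by 1/√ratio, and the true size of a nominal 5% test is 2[1 − Φ(1.96/√ratio)]. At r = 0.5 the ratio is 1.0/1.5 = 0.667, the SE factor is 1.225, and the size is 2[1 − Φ(2.40)] = 0.016.

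| Return rate | Variance ratio | SE overstated by | True size |
|---|---|---|---|
| 5% | 0.917 | 4% | 4.1% |
| 10% | 0.857 | 8% | 3.4% |
| 25% | 0.750 | 15% | 2.4% |
| 50% | 0.667 | 22% | 1.6% |
| 75% | 0.625 | 26% | 1.3% |
| 100% | 0.600 | 29% | 1.1% |

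Simulated sizes at 25%, 50% and 75% return were 2.6%, 1.6% and 1.5% for the rank sum test (4,000 runs) and 1.8%, 1.7% and 0.9% for Fisher (2,000 runs). Fisher is somewhat conservative anyway: about 4% on disjoint groups in the same simulations. With unequal return the size is 3.0% if control returns at 25% and the other arms at 50%, and 0.9% the other way round.

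**The estimate is not biased.** With a gap of 0.3 SD between returners and non-returners, the true retention-minus-control difference is (1 − r) × 0.3. That is 0.225, 0.150 and 0.075 at 25%, 50% and 75% return. The simulated means were 0.225, 0.151 and 0.076.

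**Loss of power.** Assume a trait in 60% of returners and 45% of non-returners, with 50% return. Control prevalence is 0.5 × 60 + 0.5 × 45 = 52.5%, so the retention-versus-control difference is 7.5 points.

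- Assumed SE: √(0.525 × 0.475/103 + 0.60 × 0.40/206) = 0.0599.
- True SE: write the difference as 0.75B − 0.25A − 0.5C, where A is control returners (51.5), B other returners (154.5) and C control non-returners (51.5). Then √(0.5625 × 0.24/154.5 + 0.0625 × 0.24/51.5 + 0.25 × 0.2475/51.5) = 0.0486.
- Planned test: 1 − Φ((1.96 × 0.0599 − 0.075)/0.0486) ≈ 19%.
- Overlap-aware test: 1 − Φ(1.96 − 0.075/0.0486) ≈ 34%.

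Simulation gave 17% to 18% for the planned Fisher test and 32% to 33% for the overlap-aware test.

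**The case against.** The strongest reply is that little depends on these p-values. No passage uses them to choose a model, adjust an estimate or declare the groups comparable. The randomized comparisons do not involve the retention group, and the retention outcome tests already use GEE. The size of the error also depends on an unstated return rate and is slight if few people return. All of this stands, and it keeps the point minor.

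Two stronger readings are tempting. A reader might infer that the comparison is strongly biased towards finding no difference. It is not: the estimate is unbiased, and only its standard error and p-value are wrong.

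A reader might also set the planned test's 18% detection beside the 87% or so reached by comparing returners with non-returners, and blame the whole gap on the wrong test. That mixes two questions. Returners versus non-returners tests a 15-point difference, whereas the imbalance actually present between retention and control is 7.5 points. On that same difference, allowing for the overlap raises detection only to about 33%. So about 15 of the roughly 70 points come from the independence error. The rest reflects real similarity between two groups that share members. For the same reason, a returner comparison complements the retention-versus-control table and cannot replace it.

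**Conclusion.** The point holds in a limited form. Item e) applies independent-sample tests to overlapping groups, inconsistently with item c), and the resulting p-values are conservative. Under equal return of 25% to 100%, the standard error is 15% to 29% too large and the true size is 2.4% to 1.1%. In the 60% versus 45% example at 50% return, detection falls from about 33% to about 18%.

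These figures rest on assumed return rates and, for the main range, on equal return across arms. The documents do not support a claim that the estimated differences are wrong or that any efficacy result is affected. Severity: minor.

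**What to change.** In Statistical analysis item e), take the retention-versus-control demographics out of the independent-sample tests. Either show them descriptively, for example with standardized differences, or test them with a person-clustered method using working independence and robust standard errors.

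The working correlation needs to be stated. Item c) names none, and demographics barely change within a person. In five simulated datasets an exchangeable GEE estimated correlations of 0.97 to 1.09 and log odds ratios near zero (−0.08 to 0.04), against 0.28 to 0.53 under working independence.

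Add, as a separate check on selective return, a comparison of retested with non-retested participants among all those tested initially. The Wilcoxon and Fisher tests already named are valid there because the groups are disjoint.

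The cost is a sentence or two of SAP wording and one more demographic comparison to report. No new data are needed, since the demographics come from the pre-study questionnaire.

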- a. After the hemorrhage control test, all participants were given a post-trial questionnaire which assessed their perception of usefulness of the training, willingness and self-reported comfort-level in providing first response in a mass causality scenario on a Likert-type scale.
- b. Questionnaires will also be re-administered at 3-9 month retention testing, which will assess participant perception of usefulness of the training, self-reported willingness and comfort-level in providing first response in a mass causality scenario on a Likert-type scale as well as other questions relating to emergency preparedness and hemorrhage control.

i. Protocol:

- a. A reviewer will read aloud a simulated scenario describing an explosion in a public gathering. A bleeding mannequin with traumatic amputation of leg just above the knee will be present. The participant will then be directed to a nearby bleed-control box and asked to stop the bleeding. The bleed-control box will contain a combat application tourniquet (CAT). The reviewer will start timing after directing the subject to the bleed-control box.

Subjects in the control arm were directly subjected to the bleeding control test. Experimental arm 1 subjects will attend B-Con course taught by ACS trained instructors and then subjected to the test. Experimental arm 3 and 4 subjects received an audio guide and flash card in their bleed-control box respectively,

during the test. At retention testing, participants were not retrained nor had available point of care prompts.

The participants were timed until they feel that they had stopped the bleeding. Time for complete bleeding control and tourniquet application was recorded only for subject who appropriately control the hemorrhage within 7 minutes. Appropriateness of hemorrhage control was determined by correct placements of tourniquet and adequate pressure of the tourniquet as determined by attempting to forcefully slide a Kelly clamp under between the tourniquet and the extremity of the mannequin. For unsuccessful hemorrhage control, the reason for failure was recorded. No feedback was given to the participant during the test.

- b. 20 reviewers were used for the purpose of this study. All the reviewers were physicians, nurses, and EMTs, trained in hemorrhage-control.

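### The only analysis named for change in empowerment is single-group, so on its own it cannot separate an intervention effect from the effects of testing; no arm-versus-control comparison is specified

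*Combined protocol and SAP*

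**What the plan says.** Statistical analysis, item f, covers empowerment. It opens with descriptive statistics and then states "Likert type data will be analyzed using non-parametric tests (Wilcoxon sign rank, Kruskal-wallis test"). For change it states "Single group repeated measures analysis will be used to analyze the change in empowerment over time". It names no comparison of any intervention arm with control, and it does not say which groups, time point or outcome (level or change) the Kruskal-Wallis test is for.

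The design offers more than that analysis uses:

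- **Randomized control.** Under Randomization, "for every four participants, one was randomized to each of the four arms", and the control arm "received no intervention (no training or access to point-of-care prompts").
- **Baseline answers.** Under Pre-study questionnaire, "The questionnaire also included questions to determine participants willingness to assist in an emergency and self-reported comfort level".
- **Post-test answers.** Under Post-trial questionnaire, item a, "After the hemorrhage control test, all participants were given a post-trial questionnaire". Item b repeats the questions at 3-9 months.
- **Crossover.** Under Protocol, item 1, "After testing of the two point of care prompt arms and the control arm, these individuals then underwent the ACS B-Con training".

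For tourniquet application, by contrast, items a and b of the Statistical analysis section name each intervention-versus-control comparison and state that it is made as randomized.

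**The concern.** Between the pre-trial and post-trial questionnaires every participant does the bleeding-control simulation and answers the same kind of question a second time. Either could move willingness or comfort, up or down, with no contribution from the course, the audio kit or the flashcards. A single-group analysis reports the sum of these influences. If testing raises scores, the sum flatters the intervention. If a failed attempt lowers them, it can hide a real benefit. The control arm goes through the same test and the same two questionnaires, so comparing with it removes what the arms share.

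At stake is whether the empowerment results can show that each intervention raises willingness and comfort more than no intervention does. The data for that are already planned, but the named analysis of change does not address the question.

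**Working it through.** **1. Is there a figure in the plan to reproduce?** No. There is no hypothesis, effect size or sample size for empowerment. The 103 per arm under Sample size calculation was set for tourniquet application and is used below only as an arm size.

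**2. What each analysis estimates, pre-trial to post-trial.** Let S be the average change from doing the simulation and being asked twice, and E the effect of the intervention.

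- Single-group change, intervention arm: S + E
- Single-group change, control arm: S
- Intervention minus control: (S + E) − S = E

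The single-group test is a test of S + E = 0. It matches a test of E = 0 only if S = 0, which the documents give no reason to assume. This holds whether single group means each arm separately or the whole cohort pooled.

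**3. Illustration of size.** All inputs except the arm size are assumptions: a 5-point item cut from a normal latent score at −1.2, −0.4, 0.4 and 1.2; pre-post latent correlation 0.6; 103 per arm; 1000 runs; two-sided 0.05. The same shift S was given to both arms, so E = 0. Share of runs significant:

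| Common shift (latent SD) | Within-arm signed rank | Between-arm rank sum on change |
|---|---|---|
| 0 | 5.1% | 4.2% |
| 0.1 | 19.2% | 5.0% |
| 0.2 | 52.4% | 5.0% |
| 0.3 | 85.7% | 6.3% |
| 0.5 | 100% | 3.7% |

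The simulation error around 5% is √(0.05 × 0.95 / 1000) = 0.7 percentage points, so the right-hand column is consistent with 5% throughout.

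**4. Sensitivity to the assumed correlation.** Treat the score as continuous. The SD of change is √(2(1 − ρ)), and the within-arm rejection rate is about Φ(z − 1.96), with z = 0.2 × √103 / SD for a shift of 0.2.

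- ρ = 0.3: SD 1.183, z = 1.715, 40%
- ρ = 0.5: SD 1.000, z = 2.030, 53%
- ρ = 0.7: SD 0.775, z = 2.620, 75%

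For ρ = 0.6 this approximation gives 62%, against 52% in the simulation, because five categories carry less information than a continuous score. The conclusion does not depend on the correlation chosen.

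**5. What the Kruskal-Wallis test could supply.** If applied to the four arms at the post-trial questionnaire, it would be a valid randomized comparison. Three things are still missing. Its use is not stated. A four-group omnibus test does not show which intervention differs from control. It is not stated to use the pre-trial answer.

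**6. What the baseline answer adds.** It adds precision; randomization already makes a post-only comparison valid. In a linear model, adjustment multiplies the variance of the arm contrast by 1 − ρ²: 1 − 0.3² = 0.91, 1 − 0.5² = 0.75, 1 − 0.7² = 0.51, with ρ assumed. These ratios do not carry over to a proportional-odds model, where the adjusted odds ratio is also a different quantity from the unadjusted one.

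**7. Which interval the control can serve.** The control and both prompt arms receive B-Con after initial testing, so the untrained control exists only from pre-trial to post-trial, and only if the post-trial questionnaire came before B-Con. The text supports either order. The questionnaire is tied to the test, which suggests before. Yet it asks all participants how useful the training was, and control participants had received none unless B-Con had already been given.

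**The case against.** The strongest reply is that item f already contains a between-group test, and that the obvious groups in this trial are the four randomized arms. A post-test comparison of those arms would support attribution without any baseline adjustment. This stands. A reader might infer that under this plan no rise in empowerment could ever be credited to an intervention; the documents do not support that. The limitation belongs to the single-group analysis, and the remaining gap is that the between-group test is undefined and is not directed at control.

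A second reply is that change over time includes the 3-9 month point, by when every arm has been trained. This also stands. No comparison of arms at that point can isolate training from no training, so a single-group analysis there follows from the design.

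Third, a reader might infer that the arms would be judged different because one reached significance and another did not. Nothing in the plan proposes this, and single group may mean the pooled cohort.

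Fourth, the questionnaire order is unstated, which is not the same as wrong. Initial testing is described in the past tense, so it may only be possible to report the order.

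Finally, empowerment is not the primary outcome and the choice of ordinal regression is partly preference. Both are fair. They limit the weight of the point and the insistence on one model, but they do not remove the case for a stated comparison with control.

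**Conclusion.** The point holds in a limited form. The only analysis named for change in empowerment cannot, by itself, separate an intervention effect from the effects of the simulation and of repeated questioning, and the one between-group test listed is not specified well enough to do so. With no intervention effect, a common shift of 0.2 latent SD would make the within-arm test significant in roughly 40% to 75% of cases across assumed correlations of 0.3 to 0.7 (continuous approximation, 103 per arm). The between-arm test of change stayed at about 4% to 6% across all simulated shifts (correlation 0.6). Whether a shift of that size occurs is not known from the documents; the figures illustrate the mechanism and do not predict the result.

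The remedy assumes that the post-trial questionnaire preceded B-Con in the control and prompt arms. If it did not, the contrast with an untrained control is lost. The tourniquet analysis and the primary conclusion are unaffected. The change should be made because it uses data already planned and gives empowerment a randomized comparison.

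**What to change.** 1. **Initial phase.** In item f, make the main empowerment analysis a comparison of the post-trial willingness and comfort answers for each intervention arm versus control, as randomized and adjusted for the pre-trial answer, for example by ordinal (proportional-odds) regression. Report each contrast with a confidence interval.
2. **Kruskal-Wallis test.** If it is kept, state its groups, time point and outcome (level or change), and give it a supporting role.
3. **Questionnaire order.** State whether the post-trial questionnaire was completed before the crossover B-Con training. If it came after for the control and prompt arms, say that there is no contrast with an untrained control and interpret the results accordingly.
4. **Change to 3-9 months.** Keep the single-group analysis and label it uncontrolled, because every arm has had B-Con by then.
5. **Precision.** If a gain from baseline adjustment is cited, present it as a linear-model approximation under assumed correlations.

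The cost is a few sentences in item f and one on questionnaire order. No new data are needed. The empowerment analyses are written in the future tense, so their wording can apparently still change. The order of questionnaire and training may already be fixed, in which case it can only be reported.
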